3.15.1.7 Adverse Event Summaries Across Study Periods

The analyses specified in [Section 3.15.1.5](#) will be repeated based on the data across all periods (DEP, RWP, and OLE). TEAEs will be summarized across study periods by dose group: placebo, 3×10^{11} , 6×10^{11} , 1×10^{12} and SYNB1934v1 overall. The dose group will be determined by the dose the participant was on at the TEAE start date.

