### **3.2.3. Part 3: Open-Label Extension**

During the OLE, all participants will complete a dose ramp to their iTD over time guided by tolerability, as described for the DEP, including the full dose ramp schedule (Table 4). The iTD in OLE may be different from the iTD in DEP or RWP. The investigator may escalate the dose of SYNBI934v1 up to a maximum of  $1 \times 10^{12}$  live cells based on tolerability; multiple attempts to escalate to a higher dose level are permitted per investigator discretion.

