**Table 5: Schedule of Events: Dose-escalation (Part 1) and Randomized Withdrawal (Part 2)**

Description/Week a	Screen b	DEP (Part 1)			RWP (Part 2)		
		Study/DEP Baseline	iTD-Finding Period	End of DEP b (RWP Baseline) c	Wk 1	Wk 3	Wk 4 (OLE Baseline) c
Study Day	-45 to -1	1	Up to 105 days d	21 days after iTD	7	21	28
Assessmentb (Protocol Section)							
Informed consent (11.5)	•						
Medical history and prior medications (5.2)	•						
Vital signs (SBP/DBP, pulse, body temperature, height, weight e ) (5.5.2)	•	•		•			•
Physical examination (5.2)	•						
FSH test (postmenopausal women only) (5.5.3)	•						
Pregnancy test (WOCBP only) f (5.5.3)	•	•		•			•
Record concomitant medications (4.3.4)	•	•	•	•	•	•	•
Adverse event reporting (5.5.1)	•	•	•	•	•	•	•
Collection of adverse event diary cards (5.5.1)		•	•	•	•	•	•
Weekly contact by site personnel (telephone, text, email)			•	•	•	•	•
Randomization (8.11)				•			
Blood Phe g and Tyr (5.4.1)	•	•	•	•	•	•	•
3-Day dietary intake assessment h (3.3)		•	•	•	•	•	•
Administer PPI once per day (4.3.4.1)	• i	•	•	•	•	•	•
IMP immediately after meals j (3.2)		•	•	•	•	•	•
Laboratory tests (hematology/CBC with differential, CRP, serum chemistry, urinalysis) (5.5.3)	•	•		•			•
Electrocardiogram (supine for 5 minutes)(5.5.2)	•						
Immunogenicity sample k (5.2)		•					
Optional fecal sample for microbiome analysis l (5.2)	•						

AE = adverse event; CBC = complete blood count; CRP = C-reactive protein; DEP = dose-escalating period; DBP = diastolic blood pressure; FSH = follicle-stimulating hormone; IMP = investigational medicinal product; iTD = individually titrated dose; Phe = phenylalanine; PPI = proton pump inhibitor; RWP = randomized withdrawal period; SBP = systolic blood pressure; Term = termination; Tyr = tyrosine; WOCBP = women of childbearing potential.

a Weeks are relative to the study period (i.e., each part begins with Week 1). All assessments/visits may be conducted within a 3-day window.

b All visits/assessments may be performed in the clinic or by a home healthcare professional at an alternate location (e.g., home, office, etc.), except for screening and end of DEP which must either be in person or via a virtual platform capable of completing all scheduled events including examination.

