c Participants who discontinue prematurely during the DEP will complete an early termination visit 30 days after the last dose of IMP as described in Table 6. Participants who discontinue prematurely during RWP will complete RWP study measures as scheduled prior to the early termination visit. Early termination visits are described in Section 5.6.

- d Participants may titrate down to the previous dose level during the iTD period if there is difficulty tolerating a higher dose level or at the investigator's discretion. Visits and blood draws occur after a participant has been at a dose level for 3 weeks (including the ramp of that dose level as shown in [Table 4](#)). Participants must remain on their iTD for 3 weeks before proceeding to Part 2. Participants cannot up-titrate again until the OLE.
- e Height and weight measured only at screening.
- f Serum pregnancy test at screening; urine pregnancy test at other visits.
- g All blood Phe should be drawn in duplicate. Baseline samples in DEP and RWP must be taken prior to the first doses in those periods. In Part 1, blood Phe will be measured every 3 weeks after a change in dose level during the iTD-finding period. In Part 2, blood Phe will be measured at Weeks 1, 3, and 4. See [Section 5.4.1](#) of the protocol for more information. Patients enrolled in the optional DEP weekly substudy will have weekly [REDACTED] See [Section 5.4.2](#) of the protocol for more information.
- h A 3-day dietary intake assessment will occur for 3 consecutive days prior to scheduled study visits and blood Phe draws. See Diet Manual for more information.
- i The first dose of a PPI will be taken on or before Day -7 and continue daily as described in [Section 4.3.4.1](#).
- j Investigational medicinal product should be taken within 30 minutes of finishing a meal. See the Diet Manual for further details.
- k Samples will be used for monitoring anti-drug antibodies as needed (see [Section 6.3](#)).
- l Fecal samples can be done at any time during the screening period, no less than 5 days prior to baseline visit.

**Table 6: Schedule of Events: Part 3, Open-Label Extension Period and Follow-up, End of Study and Early Termination Visits**

	Quarterly Visits	End of Study	Early Term.
	Every 90 days ± 5 days	at least 30 days after last dose	at least 30 days after last dose
Assessmenta (Protocol Section)			
Vital signs (SBP/DBP, pulse, body temperature) (5.5.2)	•	•	

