### 5.5. Safety Assessments

#### 5.5.1. Adverse Events

Adverse events will be assessed continuously by direct observation and participant interviews. For GI AEs, participants will also fill out a diary card during screening, DEP, and RWP to allow for enhanced capture of these AEs. The diary cards will be collected at each scheduled visit, excluding the initial screening visit and visits associated with the weekly substudy. The severity of AEs will generally be evaluated using the National Cancer Institute Common Terminology Criteria for Adverse Events (CTCAE), v5.0, with exceptions described in Section 6.1.1.1. All AEs occurring from the time a participant signs the ICF through the follow-up period will be recorded, regardless of causal assessment to IMP.

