3.15.1.8 GI Daily Diary Card

As discussed in Section 5.5.1 of the study protocol, participants will fill out a diary card during screening, DEP, and RWP to allow for enhanced capture of the gastrointestinal (GI) AEs. This diary will contain the GI event description start/stop date and the question “*how much did this event bother you?*” with the response being a 0–10-point numeric rating scale with 0 bothered” and 10 bothered”. When the investigator records this event as an AE, the following summaries of the tolerability will be performed:

- For GI TEAEs with a start date in the Screening Period, the tolerability will be summarized by PT and overall.
- For GI TEAEs with a start date in the DEP, the tolerability will be summarized by PT and overall, for each iTD and overall.
- For GI TEAEs with a start date in the RWP, the tolerability will be summarized by PT and overall, for treatment group, and with the active arm, for each iTD and overall.

Note: the other information provided in the GI Daily Diary Card will be incorporated in the adverse event database. For AEs occurring over multiple days, the highest bothersomeness score will be recorded. Should the investigator determine that the event recorded on the daily diary card is not an adverse event, the corresponding GI Daily Diary card entry, including the bothersomeness data, will not be recorded in the adverse event database.

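### The all-period adverse event tables in SAP 3.15.1.7 set placebo time fully covered by the GI diary and weekly contact against active time that includes a long OLE with neither, so their pooled GI comparison cannot be interpreted

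*SAP*

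**What the plan says.** **How GI events are collected.** Protocol 5.5.1 says "participants will also fill out a diary card during screening, DEP, and RWP to allow for enhanced capture of these AEs". SAP 3.15.1.8 gives the same three periods and adds that, apart from the bothersomeness score, "the other information provided in the GI Daily Diary Card will be incorporated in the adverse event database", provided the investigator judges the entry to be an adverse event. Protocol Table 5 (DEP and RWP) has a row "Collection of adverse event diary cards (5.5.1") and a row "Weekly contact by site personnel (telephone, text, email"). Protocol Table 6 (OLE) and its SAP counterpart, Table 12, have neither row; OLE visits are set at "Every 90 days ± 5 days".

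**What happens in the OLE.** Everyone is on active drug. Protocol 3.2.3 has participants repeat the full dose ramp, and "multiple attempts to escalate to a higher dose level are permitted per investigator discretion". Protocol 3.1 and SAP 2.2 also allow new participants to be enrolled straight into the OLE.

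**How events are tabulated.** SAP 3.15 presents safety separately for each period, and then also across periods. Under 3.15.1.7 the summaries of 3.15.1.5 "will be repeated based on the data across all periods (DEP, RWP, and OLE"), in columns for placebo, each of the three dose levels, and active overall. Those summaries are numbers and percentages of participants with an event. Section 3.15.1.7 does not restrict them to time with the diary, adjust for exposure, or mention the difference in collection.

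**The concern.** The protocol describes GI tolerability as what limits dosing (1.6, 1.7), and by its own account the diary is there to pick up more GI events. A table that puts placebo next to active drug over all periods compares a group observed entirely with the diary and weekly contact against one observed partly, and possibly mostly, without them. The OLE is also where the ramp is repeated: the scheduled ramp in SAP Table 8 runs to week 9 (63 days), before the first quarterly visit (day 85 at the earliest). Anyone enrolled directly into the OLE would have no time on drug with the diary at all.

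The pooled tables could therefore be read as evidence on GI tolerability against placebo, or across dose levels, when the columns differ in how events were found and in how long participants were followed.

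**Working it through.** The documents give no figure on this point, so there is nothing to reproduce. The check is person-time arithmetic.

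**Inputs.** DEP about 3 to 15 weeks, all active (SAP 2.2). RWP 4 weeks, 1:1, the only period with placebo. OLE up to 36 months, all active; 36 months = 156.5 weeks. The 9-week DEP corresponds to the uninterrupted ramp in SAP Table 8.

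**Formula.** Take one pair of randomized participants, one per arm, both entering the OLE.

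- Active weeks with diary = 2 × DEP + 4
- Active weeks without diary = 2 × OLE
- Placebo weeks = 4, all with diary
- Share of active time without diary = 2 × OLE / (2 × DEP + 4 + 2 × OLE)

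Example, 15-week DEP and 36-month OLE: 313.1 / (34 + 313.1) = 313.1 / 347.1 = 90.2%.

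| Mean OLE time | DEP 3 wk | DEP 9 wk | DEP 15 wk |
|---|---|---|---|
| 3 months | 72.3% | 54.3% | 43.4% |
| 6 months | 83.9% | 70.3% | 60.5% |
| 12 months | 91.3% | 82.6% | 75.4% |
| 36 months | 96.9% | 93.4% | 90.2% |

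The corresponding share of placebo time is 0% in every cell.

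**Break-even.** The share reaches one half when 2 × OLE = 2 × DEP + 4, that is, OLE = DEP + 2 weeks: 5, 11 and 17 weeks for a DEP of 3, 9 and 15 weeks.

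**Direction.** This is an illustration under assumptions that are not in the documents: the same true GI hazard in both groups (0.01 per week, constant), a 15-week DEP, a 36-month OLE, and OLE capture equal to a fraction f of capture with the diary.

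- Rate per week, active to placebo = (34 + f × 313.1) / 347.1. For f = 1, 0.5, 0.25 this is 1.00, 0.55, 0.32.
- Percentage with an event, placebo = 1 − exp(−0.01 × 4) = 3.9%.
- Percentage with an event, pooled active = mean over the two arms of 1 − exp(−0.01 × (a + f × 156.5)), with a = 19 weeks (active in RWP) or 15 weeks (placebo in RWP). For f = 1, 0.5, 0.25 this is 82.4%, 61.4%, 42.9%.
- The same percentage over DEP + RWP only = mean of 1 − exp(−0.19) and 1 − exp(−0.15) = 15.6%.

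With no true difference, a per-time reading favours the drug and the crude percentage counts heavily against it. Neither reading is usable.

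**The case against.** The case against has real substance.

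- **The planned statistic is incidence, not a rate.** A reader might infer that the pooled tables make the drug look better tolerated than it is, or make doses with more OLE time look safest. The documents do not support this. Section 3.15.1.7 repeats only the participant-incidence tables of 3.15.1.5; the per-day rates are in 3.15.1.6, for the DEP only. For someone already exposed to a dose, further follow-up can add an event but never remove one, so longer active time generally pushes the crude percentage against the drug. This stands: no direction should be claimed, and any apparent rate ratio rests on a capture fraction that the documents do not give.
- **The fair comparison is already planned.** The RWP tables compare active with placebo concurrently under the same collection, and the OLE is tabulated separately. This stands. A reader might infer that the safety evaluation as a whole is compromised; it is not. The problem is confined to the cross-period tables.
- **The OLE still collects adverse events.** Protocol 5.5.1 keeps observation and interview going throughout, and Grade 3 or higher GI events are AESIs reportable within 24 hours (6.3, 6.4). This stands. The end of weekly contact is inferred from its absence from the OLE schedule, and the size of the diary's gain in capture is unknown.
- **36 months is a maximum.** With a 15-week DEP and only 3 months of OLE, 43.4% of active time is uncovered. So whether most of it is uncovered depends on the data cut.

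None of this makes the pooled GI columns comparable. Two opposing distortions of unknown size do not cancel.

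**Conclusion.** The point holds in a limited form. In the tables of SAP 3.15.1.7, all placebo time has the GI diary and scheduled weekly contact, while no OLE time has either. Most active time is uncovered once mean OLE time exceeds about 17 weeks (15-week DEP) or 11 weeks (9-week DEP). The pooled GI comparison with placebo, and between doses with different OLE time, cannot be interpreted in either direction.

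The coverage shares assume that both members of the pair enter the OLE and stay for the stated mean time. The diary bears on GI terms, and on overall TEAE counts so far as GI events drive them; weekly contact could affect any event. SAEs, AESIs and discontinuations should depend little on either. This is a worthwhile, inexpensive improvement to a descriptive table and does not threaten the trial's main safety comparison.

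**What to change.** In SAP 3.15.1.7:

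1. Limit cross-period GI TEAE tables that carry a placebo column, and overall TEAE tables driven by GI events, to DEP plus RWP.
2. Show OLE-inclusive versions for the active dose groups only, without a placebo column, with a footnote that the OLE was collected without the GI diary or scheduled weekly contact.
3. State that a fall in GI events from DEP to OLE cannot by itself be read as improved tolerability. This does not rule out real adaptation; it says that this table alone cannot show it.
4. Keep all-period pooling for SAEs, AESIs and discontinuations, with exposure time shown per column.

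The cost is SAP wording and one extra table split. The limit of the fix is that DEP plus RWP equalises the collection tool but not blinding or length of exposure. In the illustration above, equal hazards still give 15.6% on active against 3.9% on placebo over those two periods, so the within-RWP table remains the one to use for comparison with placebo.

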### **3.6. Duration of Study Participation**

The maximum time of study participation for a participant is planned to be approximately 6 months for screening through RWP and up to 36 months for Part 3:

- Screening: up to 45 days
- Part 1 (DEP): up to 15 weeks
- Part 2 (RWP): 4 weeks
- Part 3 (OLE): up to 36 months

The clinical trial concludes with the final visit of the OLE (36 months). No additional arrangements are made for the care of subjects following the completion of the trial, as they will be returned to the standard of care for PKU.

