2.2 STUDY DESIGN

This is a 3-part, Phase 3 study consisting of a dose-escalating, open-label period (DEP; Part 1) of up to 15 weeks, followed by a 4-week, double-blind, placebo-controlled, randomized withdrawal period (RWP; Part 2), and an open-label extension (OLE; Part 3) of up to 36 months. [Figure 1](#) presents a study schematic.

In the DEP, all enrolled participants will maintain a stable diet reflecting their baseline Phe intake and receive escalating doses of SYNB1934v1 from approximately 3 to 15 weeks to determine an iTD, which is defined as the highest dose the participant is able to tolerate. A participant will be defined as having reached an iTD if they tolerate 3 weeks at a dose, regardless of whether other doses are tolerated.

Blood Phe level will be measured at each dose level after 3 weeks at that level. A responder will be defined as a participant who achieves a $\geq 20\%$ reduction in blood Phe level compared to DEP baseline on their iTD. For inclusion in the RWP primary efficacy analysis population, response will be assessed at the third week of a participant's established iTD for SYNB1934v1.

If at any time during a 3-week dosing interval in the DEP the participant or investigator considers a dose level to be intolerable, the dose may be de-escalated after discussion with the medical monitor. In this case, the participant will restart 3 weeks at the lower level iTD. After de-escalation, participants cannot escalate to a higher dose again during.

[figure not shown]
The DEP will contain an optional substudy (DEP weekly substudy) to evaluate the range and variability of [REDACTED] at each dose level. The [REDACTED] participants in this substudy will have weekly Phe and Tyr value assessments during the DEP (i.e., with Tyr assessments being primarily assessed for safety).

Once the first [REDACTED] participants have attained an iTD and completed the DEP or the [REDACTED] has a baseline DEP and has been in the study for [REDACTED], whichever occurs earlier, the DEP data will be evaluated by an independent Data Monitoring Committee (DMC). The DMC will use a pre-specified set of criteria based on both safety and efficacy to determine whether the dose regimen is appropriate or whether any doses should be discontinued as well as whether the study should be stopped for futility. Enrollment will not be paused during the interim analysis.

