2.2.2 Randomization and Blinding Procedures

In the RWP, participants will be randomized in a 1:1 ratio to receive either SYNB1934v1 or matching placebo, stratified on screening Phe level ([REDACTED] Participants, investigators, and the sponsor will be blinded to randomized IMP assignment during the RWP. In the case of an emergency where information regarding treatment assignment would impact the care provided to a participant during the RWP of the study, the investigator will have immediate access to unblind the treatment code in the interactive response system (IXRS). The instructions for unblinding a participant in the IXRS can be found in the IXRS User Guide. In the event unblinding is necessary, the investigator is strongly encouraged to contact the medical monitor to discuss the situation and the participants medical status prior to unblinding. It is mandatory that any personnel involved in the unblinding or who have access to the unblinded treatment assignment maintain the confidentiality of the information.

During the DEP and RWP a participant's blood Phe levels will be blinded to the participant, investigator and sponsor. During the DEP and RWP, the investigator will receive an email alert from the central laboratory if a blood Phe is $> 1.5 \times$ the DEP baseline, if Phe is $< 30 \mu\text{mol/L}$, or if Tyr is $< 20 \mu\text{mol/L}$. After the receipt of one of these trigger values, the investigator should arrange for a retest of Phe and Tyr. If the trigger value is confirmed to be out of range, the individual participant will be discontinued from the study.

The DEP overall responder rates and DEP baseline Phe values as well as the group-level DEP interim analysis results will be provided to the sponsor by the DMC.

Both the CRO's blinded and unblinded teams will have access to the participant-level blood-Phe levels.

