3.13.2 Treatment Duration

For each of the 3 study periods treatment duration will be Last dose date – First dose date + 1.

For each of the 3 study periods (DEP, RWP, and OLE), treatment duration will be summarized using the SAS populations (defined in [Section 3.5](#)), with results also being presented by responder/nonresponder and treatment group within responder/nonresponder subgroups for the RWP and OLE.

Additionally for the DEP, the duration of time (i.e., days) that a participant was on a dose level that the participant discontinued from will be summarized by dose level and overall.

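### The pooled adverse event tables in SAP 3.15.1.7 set crude incidence on 28 days of placebo beside crude incidence on up to about 40 months of active drug, with no participant-time, so their columns are confounded with time at risk.

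*SAP*

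**What the plan says.** SAP 3.15.1.7 states that the analyses of 3.15.1.5 "will be repeated based on the data across all periods (DEP, RWP, and OLE"). The columns are given as "TEAEs will be summarized across study periods by dose group: placebo", then each of the three dose levels and SYNB1934v1 overall. Events are assigned to columns by this rule: "The dose group will be determined by the dose the participant was on at the TEAE start date". The analyses being repeated are counts and percentages of participants with at least one event, including those for serious events, events of special interest, and events leading to discontinuation. Section 3.15.1.7 does not define the percentage denominator for the pooled columns.

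Exposure by part:

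- **DEP:** everyone receives SYNB1934v1, "from approximately 3 to 15 weeks to determine an iTD" (SAP 2.2).
- **RWP:** "Part 2 (RWP): 4 weeks" (Protocol 3.6). Allocation is 1:1 to active drug or placebo (SAP 2.2.2), and this is the only part in which placebo is given.
- **OLE:** everyone receives SYNB1934v1, "Part 3 (OLE): up to 36 months" (Protocol 3.6).

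The only time-based adverse event rate in the SAP is the per-day rate in 3.15.1.6, which covers the DEP dose-ramp periods. In 3.13.2, for each study period, "treatment duration will be summarized using the SAS populations". No participant-time pooled over the three parts by dose group is specified.

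**The concern.** Crude incidence rises with time at risk even when the event rate does not change. A table with 28 placebo days in one column and possibly years of active drug in the next can therefore show an excess on active drug when there is none.

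The dose columns have the same problem. A level passed through during escalation is held for about 3 weeks (SAP Table 8), while the dose a participant settles on in the OLE may be taken for years.

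At stake is how the pooled table is read, including its rows for serious events, events of special interest and discontinuations. The SAP specifies no participant-time by dose with which a reader could correct the percentages.

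**Working it through.** **1. Stated durations.** Screening up to 45 days, DEP up to 15 weeks and RWP 4 weeks give 45 + 105 + 28 = 178 days, or 178 / 30.4375 = 5.8 months. This agrees with the approximately 6 months in Protocol 3.6.

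**2. Maximum exposure.** OLE: 36 × 30.4375 = 1,096 days.

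- Active, for a participant on active drug in the RWP: 105 + 28 + 1,096 = 1,229 days (about 40 months), or 1,229 / 28 = 44 times the placebo time.
- Active, for a participant on placebo in the RWP: 105 + 1,096 = 1,201 days, or 43 times.

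**3. Effect on crude incidence.** The documents give no event rates, so these inputs are assumptions:

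- a constant event rate, identical on placebo and active drug;
- a 28-day risk p of 1% to 10%;
- 63 DEP days (three levels of 21 days);
- an average of 14 active RWP days per participant (half of 28, from 1:1 allocation);
- 0, 12 or 36 months of OLE.

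Daily rate: λ = −ln(1 − p) / 28. Crude incidence over t days: 1 − exp(−λt).

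For p = 5%, λ = 0.05129 / 28 = 0.001832 per day:

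- no OLE, t = 63 + 14 = 77: 1 − exp(−0.141) = 13%;
- 12 months of OLE, t = 77 + 365 = 442: 1 − exp(−0.810) = 56%;
- 36 months of OLE, t = 77 + 1,096 = 1,173: 1 − exp(−2.148) = 88%.

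| Placebo, 28 days | Active, no OLE | Active, 12-month OLE | Active, 36-month OLE |
|---|---|---|---|
| 1% | 2.7% | 15% | 34% |
| 5% | 13% | 56% | 88% |
| 10% | 25% | 81% | 99% |

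The true rate ratio is 1.0 in every cell. If 30% per year leave a planned 36-month OLE (mean active time about 750 days), 5% on placebo becomes 67% on active drug.

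**4. Briefly held doses.** A participant who passes through 3 × 10^11 once in the DEP and once in the OLE ramp spends about 21 + 21 = 42 days there: 1 − exp(−0.001832 × 42) = 7.4%, against 5% on placebo. With only 21 active days the figure is 3.8%, below placebo.

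**5. What an exposure-adjusted rate does.** Under a constant equal rate, first events divided by time to first event or end of exposure estimates λ in every column, so the ratio is 1.0. Under an early effect it dilutes. Take λ as above, tripled for the first 28 active days and then back to background, over 1,200 days:

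- event-free at day 28: 0.95³ = 0.857;
- event-free at day 1,200: 0.857 × exp(−0.001832 × 1,172) = 0.100, so 0.900 have an event;
- mean time at risk: 0.143 / 0.005496 + 0.857 × 0.883 / 0.001832 = 26 + 413 = 439 days;
- rate: 0.900 / 439 = 0.00205 per day, and 0.00205 / 0.001832 = 1.12.

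A threefold early excess shrinks to a ratio of about 1.12.

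**The case against.** The case for leaving the table alone has several parts.

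- **It is supplementary and descriptive.** SAP 3.15 presents safety separately for each part and adds the pooled display afterwards. Section 3.15.1.7 specifies no test, difference or ratio.
- **A valid comparison already exists.** The RWP tables in 3.15.1.5 set active drug against placebo under randomization, over the same planned 4 weeks.
- **The rate may not be constant.** The Protocol says that most adverse events have been gastrointestinal (1.7) and that titration improved tolerability (1.6), which suggests early clustering. Diary capture of gastrointestinal events covers screening, DEP and RWP only, so reporting may fall in the OLE.
- **OLE time may be short.** Thirty-six months is a maximum, and DEP and RWP are analyzed once all participants have completed the RWP (SAP 2.2.3).
- **The shells are a separate document** (SAP 3.19), so printed exposure in the column headers cannot be ruled out.

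Most of this stands, and it limits the point. A reader might infer that the safety evidence as a whole is biased against the drug, or that a large false drug effect is certain. The documents do not support either reading: the randomized RWP tables are untouched, and the size depends on event timing and on OLE time accrued. Nor is every active column inflated, as the 42-day and 21-day cases show.

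What does not stand is that the per-period tables repair the pooled one. They leave its columns unequal in time at risk, and the SAP text supplies no pooled participant-time by dose.

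**Conclusion.** The point holds for the pooled tables of SAP 3.15.1.7 and goes no further. As specified, both comparisons that those tables display are confounded with time at risk. With a constant, equal rate and a 28-day placebo risk of 5%, the apparent incidence on active drug is about 2.6 times placebo with no OLE data (13% against 5%) and about 18 times with a full 36-month OLE (88% against 5%). These figures rest on the assumed rate, 77 days of DEP and RWP active time, and the OLE time shown. Early clustering would reduce them.

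Participant-time alone would not make the pooled placebo column comparable. Participants enter the RWP only after completing 3 weeks at their iTD, whereas the active columns also include people who did not tolerate dosing. No primary or key secondary efficacy analysis is affected.

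**What to change.** Amend SAP 3.15.1.7 as follows:

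1. Define the denominator of each active dose column as participants who received at least one dose at that level.
2. Print total participant-time in each column header.
3. Beside the crude counts for the active dose columns, add exposure-adjusted incidence: participants with a first event divided by participant-time at that dose up to the first event or the end of exposure, with a 95% confidence interval.
4. Drop the placebo column from the pooled crude table, or label it as RWP-only, and refer readers to the RWP table for the placebo comparison.
5. State that the average rate is to be read with the ramp-period rates of 3.15.1.6, or split it by time since starting the dose.

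The cost is SAP wording, programming and extra table columns. Start and stop dates by dose level are already on the study drug administration CRF (SAP 3.13.1), so no new data are needed. The downside is that one average rate over a long exposure can dilute early, ramp-related gastrointestinal events, which is why item 5 is needed and why the crude counts should stay for the active doses.
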